10.5. Visit 6 (Week 12)

Visit 6 should occur after 12 weeks of double-blind study drug treatment, scheduled at Day 84 -5 / +7 days. The following assessments and procedures are to be completed in the following general order:

- Collect study drug and assess compliance
- Assess occurrence of adverse events
- Update concomitant medications
- Obtain vital signs and weight
- Administer CAPS-5-“Symptom Severity Version” using 1-week recall
- Conduct urine pregnancy test (for women of child-baring potential). Serum pregnancy test may be done at Investigator’s discretion.
- Draw samples for clinical laboratory tests for:
 - Chemistry and hematology
- Perform visual examination of oral cavity

- Have the patient complete the following outcome scales (in order):
 - SDS
 - PROMIS scale for sleep disturbance
 - PGIC
 - CSFQ-14
- Administer the MADRS
- Administer C-SSRS-Since Last Visit Version
- Physician to assess CGI-S and CGI-I (needs to be completed once all other assessments are available for investigator to review)

10.5.1. Early Termination (ET)

In accordance with the Declaration of Helsinki, patients have the right to withdraw from the study at any time for any reason, and they will be advised of this right. The investigator and Tonix also have the right to remove patients from the study. Specific reasons for removal of a patient from the study could include, but are not limited to:

- An adverse event (AE)
- An illness that, in the judgment of the investigator or Tonix, might invalidate the study results or place the patient at risk
- The request of the patient, investigator, or Tonix, whether for administrative or other reasons
- Pregnancy

This study will attempt to obtain as complete information as possible on all participating patients. An effort must be made to contact the medical monitor prior to any patient's early termination. Each reason for early termination will be adjudicated. Patients who wish to terminate their participation in the study should be instructed to come to the clinic for an Early Termination Visit. The purpose of the Early Termination visit is to obtain critical information about the patient's participation, and should be scheduled preferably before there has been a substantial lapse in study medication usage. However, even if there has been a medication lapse, the patient should be encouraged to return to the clinic for this visit, and should be instructed to return all study medication. NOTE: These visit procedures are not intended for patients who fail to qualify for randomization or for any other reason withdraw from the study prior to receipt of a dose of double-blind study drug.

If the patient withdraws prior to the Week 2 (Visit 3) visit window (before Day 11), the following assessments and procedures are to be completed at this visit in the following general order:

- Document reason for early termination. The investigator should carefully assess the role of adverse events and/or lack of efficacy when determining the most accurate reason for the patient's early termination.

- Collect study drug and assess compliance
- Assess occurrence of adverse events
- Update concomitant medications
- Obtain vital signs and weight
- Conduct urine pregnancy test (for women of child-bearing potential). Serum pregnancy test may be done at Investigator's discretion.
- Draw samples for clinical laboratory tests for:
 - Chemistry and hematology
- Perform visual examination of oral cavity
- Have the patient complete the following outcome scales (in order):
 - CSFQ-14
- Administer the MADRS
- Administer C-SSRS – Since Last Visit Version

If the patient withdraws after the Week 2 (Visit 3) visit window (on or after Day 11), the following assessments and procedures are to be completed at this visit in the following general order:

- Document reason for early termination. The investigator should carefully assess the role of adverse events and/or lack of efficacy when determining the most accurate reason for the patient's early termination.
- Collect study drug and assess compliance
- Assess occurrence of adverse events
- Update concomitant medications
- Obtain vital signs and weight
- Administer the CAPS-5-“Symptom Severity Version” using 1-week recall
- Draw samples for clinical laboratory tests for:
 - Chemistry and hematology
 - Serum pregnancy test (for women of child-bearing potential)
- Conduct visual examination of oral cavity
- Have the patient complete the following outcome scales (in order):
 - SDS
 - PROMIS scale for sleep disturbance
 - PGIC
 - CSFQ-14

- Administer the MADRS
- Administer C-SSRS- Since Last Visit Version
- Physician to assess CGI-S and CGI-I (needs to be completed once all other assessments are available for investigator to review)

Once these assessments have been completed, the patient may be discharged from the study, provided that there is no need for additional follow-up to continue to monitor an adverse event or other condition.

10.5.2. Unscheduled Visits

Patients may need to be seen at other times than the scheduled study visits for additional safety assessments or to follow-up, as medically necessary, on clinical laboratory results, physical examination, or other findings. If an additional study visit is warranted, or occurs, the date and nature of the visit will be documented in the CRF and in the source documents.

Patients who call to report an oral AE that is a lesion of some form should be brought back to the clinic for an unscheduled oral exam if deemed appropriate. In the case in which the AE is solely sensory in nature (such as oral hypoesthesia) *and* the patient reports there is no discernable associated lesion, an unscheduled oral exam is not required but may be arranged if the investigator determines it to be clinically appropriate.

10.6. Pharmacogenomic Assessment

Patients should be offered the opportunity to participate in the pharmacogenomic assessment. The blood draw for this assessment can be done at any in-clinic visit post-Screening. It should be obtained after the patient has reviewed and signed the separate pharmacogenomic testing informed consent form, irrespective of the visit at which the main study consent is signed.

11. STUDY ASSESSMENTS

11.1. Screening Assessments

11.1.1. Psychiatric and Medical History

A psychiatric interview using the Mini International Neuropsychiatric Interview (M.I.N.I.- Version 7.0.2)([Sheehan et al, 1998](#)), a self-assessed McLean Screening Instrument for Borderline Personality Disorder (MSI-BPD) and a comprehensive medical history will be obtained at screening in order to determine whether the patient is eligible for enrollment.

While patients with mild traumatic brain injury (TBI) are eligible to participate in the study, moderate and severe TBI are excluded. Mild TBI (or concussion) is one of the most common forms of combat-related injury. Based on self-report data, approximately 15% of troops engaged in active combat in Afghanistan and Iraq may have suffered a mild TBI ([Hoge et al., 2008](#)). In the non-military population, common traumatic brain injuries result from falls, motor vehicle accidents, assaults, and sports injuries. A *history of TBI* is defined as any traumatically induced structural injury and/or physiological disruption of brain function as a result of an external force that is indicated by new onset or worsening of at least one of the following clinical signs, immediately following the event:

1. Any period of loss of or a decreased level of consciousness;
2. Any loss of memory for events immediately before or after the injury;
3. Any alteration in mental state at the time of the injury (e.g., confusion, disorientation, slowed thinking);
4. Neurological deficits (e.g., weakness, balance disturbance, praxis, paresis/plegia, change in vision, other sensory alterations, aphasia) that may or may not be transient;
5. Intracranial lesion.

Although *severity of TBI* depends in part on patient assessment in the days after a traumatic head injury, for the purposes of this protocol, mild TBI is defined as:

1. Normal structural brain imaging findings
2. Loss of consciousness not greater than 30 minutes after injury
3. Alteration of consciousness not greater than 24 hours after injury
4. Posttraumatic amnesia not more than 24 hours after injury
5. No ongoing neurological deficits (Note: tinnitus, headaches, or sleep disturbances that appeared to result from the head trauma would not be considered as ongoing neurological deficits and therefore should not be interpreted as meaning the person has a greater severity than mild TBI.)

Each incidence of traumatic brain injury in a patient's lifetime history should be assessed using these five rule outs for *greater than* mild TBI, which is exclusionary for the protocol.

In addition, the past medication history will be reviewed. Any psychiatric medication or PTSD therapies utilized during the patient's lifetime should be collected. Responses from the M.I.N.I. and MSI-BPD will serve to document the presence or suspicion of other psychiatric conditions. The diagnosis and severity of PTSD will be based on the CAPS-5 ([Section 11.2.1](#)).

11.2. Efficacy Assessments

The primary efficacy endpoint and many of the secondary and exploratory efficacy endpoints in this study are derived from clinician-administered assessments which must be administered by qualified and trained individuals at each clinical site. Study specific training will be required before staff is allowed to administer these scales. In an attempt to minimize variability in responses of a given patient over time, it is important that the same rater administer the scales to a given patient throughout the study unless absolutely unavoidable due to the rater's absence from the clinic. It is also important that the assessments, including those that are patient-completed, be conducted in the specified order, according to specific instructions, and in a setting where the patient has minimal distractions, appropriate privacy and sufficient time to complete them.

11.2.1. Clinician-Administered PTSD Scale (CAPS-5)

The CAPS-5 is an updated and validated version of a semi-structured interview that has been designed to assess the essential features of PTSD as defined by the DSM-5 ([Weathers et al, 2013](#)). The CAPS-5 affords the clinician flexibility to inquire about symptoms and diagnostic status over different time frames, such as past week, past month, and/or worst month for lifetime. For this study, a “Diagnostic” version of the CAPS-5 (lifetime and past month recall) will be utilized at the Screening visit to confirm the diagnosis of PTSD and determine eligibility based on symptom severity. A “Symptom Severity” version of the CAPS-5 (past week recall) will be completed by clinician at all other time points (Baseline [Visit 2] and after 4, 8 and 12, weeks of treatment [Visits 4, 5 and 6]). A CAPS-5 total score of 29 or above at Screening (“Diagnostic” version) and 33 and above at Baseline (“Symptom Severity” version) is requisite for eligibility.

In addition to the total symptom score, the CAPS-5 affords the opportunity to examine clusters of symptoms, including Criterion B (intrusion symptoms), Criterion C (persistent avoidance), Criterion D (negative cognitions and mood), and Criterion E (arousal and reactivity), all of which will be secondary efficacy endpoints.

The CAPS-5 interview contains the following components:

- Life Events Checklist for DSM-5 (LEC-5): Completed by the patient at Screening Visit 1 only) and reviewed by the rater of the CAPS-5 interview at the start of the interview.
- PTSD Symptoms
 - Criterion A: the rater will review the patient-completed LEC-5 and then inquire into the qualifying index trauma (Criterion A) utilizing the study-specific Criterion A - Assessment Form (CA-AF) (Visit 1 only)
 - Criterion B: Items 1-5
 - Criterion C: Items 6-7
 - Criterion D: Items 8-14
 - Criterion E: Items 15-20
 - Criterion F: Items 21-22
 - Criterion G: Items 23-25

- Global ratings: Items 26-28
- Dissociative symptoms: Items 29-30

Further instruction on when to complete each component will be provided in the study specific versions of the CAPS-5 forms.

The LEC-5, which documents the patient's lifetime traumatic experiences, will be completed by the patient at Screening Visit 1 before the clinician administered CAPS-5 (Weathers et al, 2013). The CAPS-5 rater will be responsible for reviewing the answers on this form with the patient as part of the completion of the CAPS-5 Criterion A - Assessment Form (CA-AF) in order to determine if the traumatic experience qualifies the patient for inclusion in the study. NOTE: If worst month lifetime PTSD symptoms resulted from earlier trauma(s), such as trauma(s) before age 18 or trauma(s) occurring >9 years prior to screening, the prospective patient should be excluded from participation.

At Screening, the total CAPS-5 score (Diagnostic version with 1-month recall) must be ≥ 29 and must meet the other diagnostic criteria specified in Inclusion Criterion 2 (Section 8.2) in order for the patient to continue. At Baseline (Visit 2), the total CAPS-5 score (past week recall) must be ≥ 33 .

The CAPS-5 interview must be completed by a qualified and trained rater. This rater should be kept consistent for a given patient throughout the study. If circumstances require non-conformity with the single rater approach for any patient, this should be documented. Additional information regarding the conduct, rating, and scoring of the CAPS-5 instrument as well as the requirements for rater training will be provided separately.

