13. STATISTICS

A full description of the statistical analyses to be performed at study completion will be provided in a Statistical Analysis Plan (SAP) prior to unblinding.

Baseline will be defined as those values recorded closest to, but prior to administration of the first dose of study drug.

Unless otherwise noted, significance tests of treatment differences will be tested at the two-sided 0.05 level.

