## 7. GENERAL ISSUES FOR STATISTICAL ANALYSIS

### 7.1 General Statistical Methodology

Descriptive summaries will be provided where appropriate for each of the primary and secondary variables. In general, tables will summarize data by treatment group and visit.

Baseline characteristic and safety tables will be completed for the Safety Population unless otherwise specified. Efficacy tables will be presented for the mITT Population.

Continuous, quantitative, variable summaries will include the number of participants (N) with non-missing values, mean, standard deviation (SD), median, minimum, and maximum.

Categorical, qualitative, variable summaries will include the frequency and percentage of participants who are in the particular category. In general, the denominator for the percentage calculation will be based upon the total number of participants in the study population for the treatment group unless otherwise specified.

Baseline values are defined as the last non-missing measurement prior to the first dose of study drug. Change from baseline will be defined as the post-baseline visit value minus the baseline value.

ET participants will only be followed if required to monitor an on-going adverse event or other condition.

Participants are not supposed to change study sites; however, should this be necessary to allow a participant to continue in the study, participants will be analyzed under the site where they were initially enrolled.

Study day after first dose is defined as assessment date – first dose date +1. Dates prior to first dose are defined as assessment date – first dose date.

All analyses will be performed using Statistical Analysis System (SAS®) Software version 9.4 or later.

Unless otherwise noted, 95% confidence intervals will be presented for statistical tests.

For the purposes of analyses that include a site covariate, sites that have two or fewer subjects will be pooled into a single site. If there are further problems with model convergence, other small sites causing issues will be included in this pooled site.

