### **8.3 Demographics and Other Baseline Characteristics**

Descriptive summaries of the demographic and other baseline characteristics will be completed for all participants in the safety population by treatment groups, unless otherwise specified.

Descriptive summaries of demographic and other baseline conditions will include:

- Demographics (age, gender, race/ethnicity, height, weight, body mass index (BMI), family status, education, presence of current major depressive episode (MDE), current nicotine, alcohol and THC usage, and employment status). In addition to the safety population, these will also be repeated for all randomized participants and the mITT population.
- Psychiatric history (MINI 7.0.2)
- Clinician administered scales
  - C-SSRS-Baseline/Screening Version
  - CA-AF
  - CAPS-5 Assessment (Diagnostic version)

Other assessment's baseline values will be reported with their respective follow-up measures.

Medical History will be coded using Medical Dictionary for Regulatory Activities (MedDRA) version 21.0 and summarized by System Organ Class (SOC) and Preferred Term using frequency counts by treatment group.

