A Mixed Model Repeated Measures (MMRM) analysis will be performed for the change from baseline in CAPS-5 total score to estimate the treatment difference at Week 12. The model will include all participants in the mITT population, and the dependent variable will be the observed change from baseline in CAPS-5 total score at each post-randomization visit. Covariates in the model will include the fixed categorical effects of treatment, site, sex, and treatment by visit interaction, as well as the continuous fixed covariates of baseline score and baseline score by visit interaction. An unstructured covariance matrix will be used to model the within-subject variance-covariance errors. The Kenward-Roger approximation will be used to estimate the denominator degrees of freedom. Should the unstructured model fail to converge, an autoregressive AR(1) covariance structure will be attempted, then finally compound symmetric should AR(1) not converge.

Missing data for participants in the mITT population will be imputed via multiple imputation (MI) ([Carpenter, 2013](#); [Mallinckrodt, 2013](#)). Ten repeats of the imputation will be performed using Markov Chain Monte Carlo (MCMC) assuming non-monotone missing. Where the study medication was discontinued due to lack of efficacy, lost to follow-up, or to an AE, missing values will be imputed drawing from the baseline values, conditioned on the non-missing post-baseline values, of all participants in the mITT population under the assumption that they are missing not at random (MNAR); covariates will include site and sex. If the study medication was discontinued for any other reason, values will be imputed within treatment group using MI under the assumption that they are missing at random (MAR) with covariates for site, sex, and the CAPS-5 score recorded at each time point (including baseline). The MAR approach will also be applied for sporadic missing values (prior to discontinuation).

The test statistic based upon the least squares (LS) mean treatment difference and associated p-value [REDACTED] will be presented for each stage.

In addition, the least squares means and 95% confidence intervals (CIs) will be calculated for the treatment difference between TNX-102 SL and placebo at each time point.

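### The Screening CAPS-5 total is collected before randomization but left out of the primary model; adding it would probably buy a small gain in precision

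*Protocol*

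**What the plan says.** Protocol 11.2.1 sets two pre-dose ratings of the 20-item total. The first uses the Diagnostic version, which "will be utilized at the Screening visit to confirm the diagnosis of PTSD and determine eligibility based on symptom severity": "At Screening, the total CAPS-5 score (Diagnostic version with 1-month recall) must be ≥ 29". The second uses the Symptom Severity version: "At Baseline (Visit 2), the total CAPS-5 score (past week recall) must be ≥ 33". Inclusion criterion 2 (Protocol 8.2) requires the first, so every properly enrolled patient has one.

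Baseline is the later of the two. Protocol 13 states "Baseline will be defined as those values recorded closest to, but prior to administration of the first dose of study drug", and SAP 7.1 states "Baseline values are defined as the last non-missing measurement prior to the first dose of study drug". The primary endpoint names Visit 2 directly.

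In SAP 9.1.1 the primary MMRM contains treatment, site, sex and treatment by visit, "as well as the continuous fixed covariates of baseline score and baseline score by visit interaction". Protocol 13.4.2 has the same continuous covariates. The Screening total is in neither list. SAP 8.3 places "CAPS-5 Assessment (Diagnostic version" among the scales summarized by treatment group at baseline.

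The missing-at-random imputation in SAP 9.1.1 runs "with covariates for site, sex, and the CAPS-5 score recorded at each time point (including baseline". It does not say whether Screening is one of those time points.

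**The concern.** A single rating is an imperfect measure of a patient's underlying severity. A second pre-randomization rating of the same 20 items usually carries some information that the first lacks. It cannot be affected by treatment, so adjusting for it is valid in a randomized comparison, and the data are collected anyway. If it predicts Week 12 beyond Visit 2, omitting it leaves the Week 12 treatment difference with a larger standard error than necessary. Only power and interval width are at stake. Validity and type I error are not.

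**Working it through.** Write S for the Screening total, B for the Visit 2 total and Y for Week 12. Because B is a covariate, modelling Y or the change from B gives the same residual variance.

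**1. The plan's own figure.** The planned 250 (125 per arm) cannot be reproduced, because the assumptions behind it are blacked out. For orientation, at two-sided 0.05 the detectable standardized effect is (1.960 + 0.842) × √(2/125) = 0.354 at 80% power and (1.960 + 1.282) × √(2/125) = 0.410 at 90%. The 80% used below is nominal, not the plan's stated power.

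**2. Formula.** Adding S to a model that already holds B reduces residual variance by g, the squared partial correlation:

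r(SY·B) = (r_SY − r_SB × r_BY) / √[(1 − r_SB²)(1 − r_BY²)], g = r(SY·B)².

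A partial correlation of 0.1 gives 1%, 0.2 gives 4% and 0.3 gives 9%. If r_SY = r_SB × r_BY, so that Screening predicts Week 12 only through Visit 2, then g = 0.

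**3. Numbers.** None of the correlations is in the documents. I assumed mean 38 and SD 9 for S and B before selection, r_SB 0.5-0.8, r_BY 0.3-0.6 and r_SY 0.18-0.6, then simulated 1.5 million candidates per case and kept those with S ≥ 29 and B ≥ 33. Patients = 250 × g. Power = Φ(2.802/√(1 − g) − 1.960).

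| r_SB, r_BY, r_SY | partial r, no selection | g, no selection | g after both entry rules | patients of 250 | 80% power becomes |
|---|---|---|---|---|---|
| 0.8, 0.5, 0.4 | 0 | 0% | 0% | 0 | 80.0% |
| 0.7, 0.4, 0.4 | 0.183 | 3.4% | 2.8% | 7 | 81.1% |
| 0.6, 0.4, 0.4 | 0.218 | 4.8% | 3.8% | 9 | 81.5% |
| 0.5, 0.5, 0.5 | 0.333 | 11.1% | 8.7% | 22 | 83.4% |

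The second row in full: (0.4 − 0.28)/√(0.51 × 0.84) = 0.183. At g = 2.8% the power is Φ(2.802/0.986 − 1.960) = 81.1%.

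**4. Role of the entry thresholds.** Selection does weaken Visit 2 as a predictor: in the last row its correlation with Week 12 falls from 0.50 to 0.36. It also narrows the Screening score, and the net effect is a smaller gain from adding Screening (11.1% to 8.7%).

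**5. Sensitivity.** A second model treats S and B as ratings of one latent severity (mean 38, SD 7, rating SD 5, slope to Week 12 of 0.8, residual SD 10; all assumed).

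- Base case: 3.8% without selection, 3.2% with it.
- Part of the Visit 2 rating deviation persists to Week 12: 1.9% (persistence 0.2), 0.9% (0.4), 0.2% (0.6).
- Rating errors at the two visits correlated 0.5: about 1.6%.
- Week 12 replaced by a random baseline value in 10% or 20% of patients, as a rough stand-in for the baseline-based imputation: 2.5% or 2.0%.

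**6. Cost in parameters.** There are three post-baseline visits, so the addition is one main effect plus two interaction terms, which is one extra slope at Week 12. The stages are fitted separately on about 125 patients each. With about 25 site terms, the variance cost is roughly 1/(125 − 25) = 1% per stage. A gain of 2-4% is then about 1-3% net.

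**The case against.** The strongest reply is that adjustment for baseline, site and sex is already a complete, prespecified choice, that no rule is broken, and that the benefit could be nil. The two ratings differ in recall period. The Visit 2 version is also the one used at Week 12, and the same rater is meant to see the patient throughout, so errors may be shared. For patients washed out of an excluded drug (Protocol 8.5 and 10.1.2), Screening may reflect a medicated state. Dropouts for lack of efficacy, adverse events or loss to follow-up are imputed from baseline values, which dilutes any gain. The interim can also add up to 120 participants.

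Most of this stands as a limit on size, and it removes any claim to a guaranteed minimum. It does not remove the likely benefit, which is zero only if Screening predicts Week 12 solely through Visit 2. Re-estimation buys power with recruitment and does not replace precision available from data in hand.

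A reader might infer three stronger things that the documents do not support:

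- That precision is lost because the Visit 2 score is cut at 33. Step 4 shows that truncation shrinks the gain, and Screening is itself cut at 29.
- That upward selection of the Visit 2 score biases the comparison. The same rule applies to both arms before randomization, so regression from the entry score is shared.
- That Screening is used for eligibility alone and is excluded from imputation. SAP 8.3 also summarizes it, and the imputation wording leaves its role open.

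**Conclusion.** The point holds as an optional improvement in efficiency. Every properly enrolled patient has a Screening total, and the primary model does not use it. Under the assumed correlations the gain is 0-9% of residual variance. Middle cases give about 2-4%, or 5-10 of 250 patients, and move a nominal 80% power to about 80.8-81.6%. Baseline-based imputation and the extra parameters take part of this back. The size rests wholly on a partial correlation that the documents do not report. The one matter that needs settling whether or not the covariate is added is whether Screening is a time point in the missing-at-random imputation.

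**What to change.** In SAP 9.1.1 and Protocol 13.4.2, add the Screening CAPS-5 total and its interaction with visit to the MMRM covariates. In the imputation text, name the Screening total explicitly as a predictor; if the covariate is not adopted, state whether Screening counts as a time point. Use the identical model for the interim statistic (Z1) and the stage 2 statistic. The change must therefore be fixed before the interim, which is the first unblinded look. Change from Visit 2 stays the endpoint, and the stage weights and data collection are unchanged. The cost is a few words in each document and about three extra parameters in each fit.
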